### **Hemoglobin:**

The hemoglobin concentration in whole blood will be determined by methemoglobin method. This is a quantitative and colorimetric technique in which total hemoglobin at alkaline pH is rapidly converted to a cyano derivative when treated with  $K_3[Fe(CN)_6]$ , which is determined by its absorbance at 530-550 nm. The color intensity at this wavelength is proportional to total hemoglobin concentration (23)

### **Retinol:**

Serum retinol will be determined by high performance liquid chromatography (HPLC). 100  $\mu$ l serum is deproteinized with methanol containing 50  $\mu$ g/dL retinyl acetate, and retinol extracted into hexane. The hexane layer is transferred to a clean vial, evaporated under nitrogen, redissolved in mobile phase and injected onto the HPLC column. Retinol is separated by reverse-phase HPLC using a C-18 column, and detected at 325 nm. Two plasma pool samples with assigned value set against a standard serum from National Institute of Standard and Technology (NIST) are run with each lot of samples and the concentration of retinol calculated based on the known concentration of retinol in the pool samples. (24,25,26)

### **Ferritin:**

Ferritin will be measured using ELISA based on anti-ferritin antibodies bound to latex reacting with the antigen in the sample to form an antigen-antibody complex (27)

### **Transferrin receptor (TfR):**

Transferrin receptor is measured using ELISA based upon double antibody sandwich method. Serum samples are diluted in buffer and pipetted into microwells pre-coated with polyclonal antibody to TfR. Horseradish peroxidase (HRP) conjugated murine monoclonal antibody specific for TfR is added to wells and incubated for two hours at room temperature. TfR binds to the polyclonal antibodies absorbed to the wells and the HRP-conjugated second antibodies bind to the captured TfR. Any unbound TfR and excess HRP-conjugate are removed from the wells by washing. Enzyme substrate (chromogen TMB) is added to the wells and through the action of HRP forms a blue product. Upon addition of an acid stop solution, the blue product is converted to yellow colour, the intensity of which is measured in a plate reader set at 450 nm (28).

## STAFF AND ORGANIZATION OF THE TRIAL:

**Bari mothers** will be recruited to participate in the study. They will receive the flour at weekly intervals, prepare the *chapattis* and distribute them to the families who are participating in the study. As a motivational factor, in return for this contribution, the bari mothers as incentives will receive a small amount of money and an additional amount of flour for her family.

**Bari person** will be assigned to keep a written record of the consumption of *chapattis* by the study participants.

**Field research assistants (FRAs)** will distribute the flour, monitor the usage of the flour in each bari, make spot checks of each bari to confirm that the *chapattis* are being prepared and consumed by the children and collect spot samples of flour/chapatti for analyses of vitamin A and iron

**Supervisors (SFRA)** will train and supervise the FRAs to ensure that they understand their job and are collecting the correct data. They will meet the FRAs at least every two weeks to monitor the progress of the study. Supervisors will maintain liaison with the investigators and laboratory personnel at Dhaka.

**Code supervisor:** One of the supervisors (SFRA) will be in charge of the dummy code (A, B etc.) for the flour to ensure that the FAs are distributing or the families receiving the correct flour.

**Co-Investigator (Field Operations Manager)** will supervise the activities of the field assistants (FRA) and the supervisors (SFRA) at the field level and maintain liaison with PI and other investigators at Dhaka.

**Co-Investigator (Operations Researcher)** will assist quality control checking, field level operations and coordination with field and laboratory.

**Co-Investigator (Scientist/clinical nutrition)** will give training to field staff on anthropometry and assist monitoring for compliance and quality control of data collection.

**Co-Investigator (Associate Scientist/pediatric nutrition)** assisting in designing the project, monitor and evaluation and trouble shooting during conduction of the study.

**Co-Investigator (Laboratory biochemist):** This co-investigator will be responsible for organizing blood collection at the field, transporting them to laboratory at Dhaka, carry out analyses, and maintain all results in a data set in PC.

**Co-PI (Senior Operations Researcher/Field coordinator)** will coordinate all field level activities including supply and logistics.

**Co-PI ([name], ICDDR,B)** will help with designing, decision making and planning of the study

**The PI:** This individual will be responsible for the overall supervision of the study, specifically checking quality control operations at the field level, and review the progress of the study. Coordination of the study at the field, laboratory and office level including data analyses and reports writing will be done by this person.

## TIME SCHEDULE:

Forming demographic listing for participant recruitment	1 month
Pretest of procedures	1 month
Recruitment and baseline observations	3 months
Mid-point sampling and data collection	1 month
Continue feeding programme	2 months
Final sampling and data collection	1 month
Data analyses / Reporting	3 months
Total	12 months

## Facilities Available

Describe the availability of physical facilities at the place where the study will be carried out. For clinical and laboratory-based studies, indicate the provision of hospital and other types of patient's care facilities and adequate laboratory support. Point out the laboratory facilities and major equipments that will be required for the study. For field studies, describe the field area including its size, population, and means of communications. (TYPE WITHIN THE PROVIDED SPACE).

The study will be conducted in rural villages of Mirsarai thana (sub-district) of Chittagong district where ICDDR,B maintains a field research station. This area has been under demographic surveillance and is considered a "low performing area" having a lower than average health statistics. A total of 88/required number of baris will be randomly selected from a total of 4875 baris to ensure an enrollment of 350 children in the age group of 6 – 15 years. Once the bari's is being selected, a census will be carried out, listing the names, ages, sex of each child between 6 and 15 years, along with other family members to ensure identification of each participant in the study.

## Data Analysis

Describe plans for data analysis. Indicate whether data will be analyzed by the investigators themselves or by other professionals. Specify what statistical softwares packages will be used and if the study is blinded, when the code will be opened. For clinical trials, indicate if interim data analysis will be required to monitor further progress of the study. (TYPE WITHIN THE PROVIDED SPACE).

The groups will be compared to ensure the comparability of the groups at the start of the study. The comparisons will include z-scores of weight-for-age (WA), height-for-age (HA) and weight-for-height (WH), hemoglobin, serum retinol, serum ferritin and serum TfR. These should be statistically similar at the start of the study. However, randomization design of the study is also expected to take care of comparability between the two groups. The same data points will be compared after three and six months of consuming *chapattis*. Within six months, it is expected that serum retinol will be significantly increased in the fortified group compared to the unfortified group. We expect that the TfR will be decreased within six months since there will be fewer binding sites available.

Outcome measures including retinol, ferritin and TfR will be compared both within and between groups from start to the end of the trial. Change in nutritional status reflected by z-scores for WA, WH and HA, although not outcome measures, will also be investigated. Means of continuous variables, if normally distributed, will be compared by Student's t test. If the data of continuous variables do not conform to a Gaussian distribution, non-parametric tests including Mann-Whitney test will be used. Difference in categorical variables will be assessed by chi-square test. The confounding will be controlled by multiple regression analyses. An analysis of covariance will be performed for comparing the final levels of the outcome variables making allowances for any difference between the initial or 3-month levels.

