status will be assessed by determining changes in serum concentrations of retinol, ferritin, transferrin receptor (TfR) and hemoglobin before and after intervention in the treatment and control groups. These markers will be the outcome measures of any change in vitamin A and iron status in the children. A mid-point blood analysis at 3 months will also be done to measure of the onset of a detectable change.

Concerned agencies may use the results of this study for planning food fortification program in Bangladesh as well as in other developing countries. It may also stimulate local food companies to come forward with new strategies in areas of fortification and take an effective role in micronutrient intervention programs. Similarly, the Government of Bangladesh may use this information to formulate policies regarding food fortification.

KEY PERSONNEL (List names of all investigators including PI and their respective specialties)

Name	Professional Discipline/ Specialty	Role in the Project
1. I. [name]	Senior Operations Researcher / Nutrition	PI
2. [name]	Director, ICDDR,B	Co-PI
3. [name]	Senior Operations Researcher / Public Health Research	Co-PI
4. [name]	Operations researcher / Public Health research	Co-Investigator
5. [name]	Associate scientist / Biochemistry Lab	Co-Investigator
6. [name]	Scientist / Clinical nutrition	Co-Investigator
7. [name]	Field Operations Manager	Co-Investigator
8. [name]	Associate Scientist / Paediatric Nutrition	Co-Investigator

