The study had a one-month pretest to establish procedures and preparation of the field settings including handling, storage of wheat flour, making of *chapattis* and see chapatti consumption pattern. Our pretest reveal that two chapattis made from 100g flour were consumed by all the 43 participants except one and well accepted when served with a condiment (halwa made of suji and sugar). This will be followed by a six month period when participant children will consume two chapattis (100 g flour) daily in addition to their usual food.

An organoleptic analysis of chapatti made from fortified flour was performed by Institute of Nutrition and Food Science, Dhaka University (INFS,DU) with a group of penalists experienced in organoleptic tests except one (21). The analyses based on hedonic scales of different parameters, reveal that chapatti made from fortified atta (flour) using hot water has a number of qualities with high acceptability.

The sampling unit will be the bari (composed of an average of five households and a population of about 30 per bari). The selected baris will be randomized to receive in a blinded manner either fortified or unfortified wheat flour and also receive a condiment (i.e., dal, suji, sugar etc.) to increase consumption compliance. Before feeding starts, measures like z-scores for weight-for-age, weight-for-height, height-for-age, blood hemoglobin, serum retinol, serum ferritin and serum transferrin receptor will be taken to see baseline comparability. The outcome measures that are expected to change in the group receiving fortified *chapatti* are serum retinol, serum ferritin and serum transferrin receptor concentrations. Also a change in hemoglobin level is expected. Each of these measures (weight, height, Hb level, serum retinol, serum ferritin, serum transferrin receptor) will be determined at the start (0 month), at the mid-point (3 months) and at the end of the trial (6 months).

Table: Level of fortificants per kg wheat flour and contribution from *chapatti* consumption (100g flour) to micronutrient requirements of children

Nutrient	Level in flour	Contribution of flour to requirements of children 6-15 years old		
		Nutrient consumed (per day)	RDA	% RDA
Vitamin A 	10,000 IU/kg	212 µg 	400 - 600 µg	53 - 35%
Iron 	66.0 mg	3.3 mg 	10 - 15 mg	33 - 22%
Thiamin (Vit. B 1 )	6.4 mg	0.64 mg	1.2 mg	53%
Riboflavin (Vit. B 2 )	4.0 mg	0.40 mg	1.0 mg	40%

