#### SAMPLE SIZE ESTIMATION:

Sample size was estimated by taken into account the *mean and standard deviation (SD) of serum retinol concentrations*. Unfortunately, there are no data on serum retinol or serum ferritin distributions in this age group in rural Bangladesh on which to base a sample size. However, in a trial in Guatemala [Arroyave et al. 1981] (22), the mean  $\pm$  SD of serum retinol concentrations were  $29.2 \pm 10.2$   $\mu\text{g/dL}$  and  $34.2 \pm 9.5$   $\mu\text{g/dL}$  before and after 1 year of supplementation with sugar fortified with vitamin A. With this level of change, we require 83 subjects in each group (5% significance level and a power of 90%).

Sample size was also estimated by taken into account the *mean and standard deviation (SD) of serum ferritin concentrations*. In a trial in Venezuela [Layrisse et al. 1996] (14), the mean  $\pm$  SD of serum ferritin concentrations were  $18.01 \pm 13.8$   $\mu\text{g/L}$  and  $25.2 \pm 15.3$   $\mu\text{g/L}$  before and after supplementation with maize and wheat flour fortified with iron. With this level of change, we require 87 subjects in each group (power of 90% and 5% level of significance).

Considering the greater of the two estimates (87 subjects), the calculated sample size has been doubled to 175 in each group to account for cluster and dropout effects. With a population of 30 in each bari in the study area and 4 eligible children (6-15 years) in each bari we require 44 baris in the experimental and 44 baris in the control group.

Sample size estimation was done by using the formula:

$$\frac{2(\text{SD})^2 \times \text{factor for } \alpha, \beta}{(\text{WD})^2}$$

Where, SD is the standard deviation and WD is the worthwhile difference between the means.

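### The plan compares outcomes within as well as between groups and does not say that only the between-group result tests the hypothesis

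*Protocol*

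**What the plan says.** The Data Analysis section of the protocol commits to two kinds of comparison in one sentence: "Outcome measures including retinol, ferritin and TfR will be compared both within and between groups from start to the end of the trial". It does not rank them. For continuous variables it states: "Means of continuous variables, if normally distributed, will be compared by Student's t test", with Mann-Whitney as the fallback for non-Gaussian data. Multiple regression is named for confounding. The section continues: "An analysis of covariance will be performed for comparing the final levels of the outcome variables", allowing for differences at the start or at three months.

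The Project Summary describes impact through changes in the markers "before and after intervention in the treatment and control groups".

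Other statements point to the between-arm contrast. Data Analysis says "it is expected that serum retinol will be significantly increased in the fortified group compared to the unfortified group". Specific Aims names serum retinol at 6 months as the primary marker.

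On what the two arms receive, Research Design and Methods says: "The selected baris will be randomized to receive in a blinded manner either fortified or unfortified wheat flour and also receive a condiment". Every child is to eat two chapattis from 100 g of flour daily on top of the usual diet. The markers are measured at 0, 3 and 6 months in both arms.

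**The concern.** A before/after test inside one arm asks whether the marker moved. It does not ask whether fortification moved it. Over six months a child's retinol, ferritin or TfR may shift because of the extra food, growth, season or laboratory drift, and all of these act on both arms. The control arm is there to remove them, and a within-arm test does not use it.

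The plan does not say which result answers the hypothesis. A report could therefore set a significant rise in the fortified arm beside a non-significant one in the control arm and be read as positive although the arms do not differ. The findings are meant to inform fortification policy, so that misreading would matter.

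The covariance analysis has a related looseness. The 3-month value is measured after randomization and during feeding, so adjusting for it could remove part of the effect under test.

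**Working it through.** **1. Is the sample size a two-arm or a within-arm calculation?** The inputs are in Sample Size Estimation, and the formula there is 2 × SD² × factor / WD². I assume a two-sided 5% level and 90% power, so the factor is (1.960 + 1.282)² = 10.51. The protocol does not state sidedness.

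- Retinol: means 29.2 and 34.2 µg/dL, so WD = 5.0. Average variance = (10.2² + 9.5²)/2 = 97.145. n = 2 × 97.145 × 10.51 / 25 = 81.7, or 82 per group (stated: 83).
- Ferritin: means 18.01 and 25.2 µg/L, so WD = 7.19. Average variance = (13.8² + 15.3²)/2 = 212.265. n = 2 × 212.265 × 10.51 / 51.696 = 86.3, or 87 per group (stated: 87).
- One-sided versions give 67 and 71 and do not match, so two-sided is the better inference.

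The stated figures therefore belong to a two-arm comparison of means. Resting inference on the between-arm contrast leaves 83, 87 and the inflated 175 per group as they are.

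**2. How easily could a within-arm test be significant with no fortification effect?** These assumptions are not in the documents: a common retinol shift in both arms, SD 10.2 µg/dL at both times, before/after correlation r of 0.3 to 0.7, 175 children per arm, and clustering ignored. The SD of change is 10.2 × √(2(1 − r)). The chance of a significant rise is p = Φ(shift × √175 / SD of change − 1.96).

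Example with r = 0.3 and shift 1: SD of change = 12.07, standard error = 12.07/13.23 = 0.912, and p = Φ(1.096 − 1.96) = 0.194.

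**3. How often would the fortified arm be significant and the control arm not?** With equal shifts and independent arms this is p(1 − p).

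| Common shift (µg/dL) | r | p | p(1 − p) |
|---|---|---|---|
| 1 | 0.3 | 0.194 | 0.156 |
| 1 | 0.5 | 0.254 | 0.189 |
| 1 | 0.7 | 0.388 | 0.237 |
| 2 | 0.3 | 0.592 | 0.242 |
| 2 | 0.5 | 0.737 | 0.194 |
| 2 | 0.7 | 0.918 | 0.075 |

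The maximum is 0.25, at p = 0.5. With a shift of 5 µg/dL, p is at least 0.999, so both arms would almost always be significant. Only a reader looking at the fortified arm alone would then be misled.

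Under the same assumptions, with clustering ignored, the between-arm test keeps its 5% error, because the common shift cancels.

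**The case against.** The strongest reply is that the protocol is already built on the between-arm contrast, and this is largely right. It words the expected retinol effect as fortified against unfortified, plans a covariance analysis of final levels, names 6-month retinol as primary and uses a two-arm formula. Describing within-arm change beside a between-arm comparison is ordinary reporting. The Project Summary sentence can equally be read as comparing changes between arms, which is valid.

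A reader might infer three stronger things that the documents do not support.

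- *That within-arm tests have equal standing with between-arm tests.* The two are named together without ranking, but no passage lets a within-arm result decide the hypothesis.
- *That the trial carries a false-positive rate of up to 25%.* That figure belongs to a decision rule the protocol never adopts. It rests on an assumed p, and the documents give no size for any common shift. Nor does the protocol state a one-directional error of 2.5% to set against it.
- *That the list of methods gives several parallel routes to a positive result.* Mann-Whitney is only a fallback for the t test, and regression and covariance analysis have stated purposes. Ranking the models could properly sit in a statistical analysis plan that is not shown.

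Regression to the mean is also a weak candidate explanation here, because children are not enrolled on low retinol.

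Two things in the protocol's own text survive this reply: the unqualified within-group comparison, and the choice of the 3-month level as a possible covariate.

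**Conclusion.** The point holds as a matter of interpretation. The protocol plans within-group comparisons without saying that they cannot test the hypothesis, and a within-arm change here has no concurrent control. The between-arm analysis is present, and no stated number is wrong.

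The size can only be illustrated. Under the assumptions shown, a common shift of 1 to 2 µg/dL would make a within-arm rise significant 19% to 92% of the time with no fortification effect. The misreading of one arm significant and the other not would then occur in about 8% to 24% of trials, with a ceiling of 25%. These figures rest on an equal non-zero shift, independent arms, an assumed correlation and no clustering. They describe a possible misuse of the results and are not a property of the stated plan.

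**What to change.** In Data Analysis, state that the primary inference is the between-arm difference in serum retinol at 6 months with its 95% confidence interval, adjusted for baseline retinol and accounting for bari, the unit of randomization. Remove the 3-month level as a covariate for that analysis. Report within-arm changes as descriptive summaries without p-values, and label the unadjusted and multiple-regression comparisons as supportive.

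This changes wording only: no extra children, samples or assays, and no change to the sample size. The cost is that formal within-arm tests are no longer reported.

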## Research Design and Methods

---

Describe in detail the methods and procedures that will be used to accomplish the objectives and specific aims of the project. Discuss the alternative methods that are available and justify the use of the method proposed in the study. Justify the scientific validity of the methodological approach (biomedical, social, or environmental) as an investigation tool to achieve the specific aims. Discuss the limitations and difficulties of the proposed procedures and sufficiently justify the use of them. Discuss the ethical issues related to biomedical and social research for employing special procedures, such as invasive procedures in sick children, use of isotopes or any other hazardous materials, or social questionnaires relating to individual privacy. Point out safety procedures to be observed for protection of individuals during any situations or materials that may be injurious to human health. The methodology section should be sufficiently descriptive to allow the reviewers to make valid and unambiguous assessment of the project. (DO NOT EXCEED TEN PAGES, USE CONTINUATION SHEETS).

---

**Overall study design:** This is planned as a cluster-randomized, double-blind, controlled trial in a rural area in Mirsarai thana (sub-district) of Chittagong district in Bangladesh. *Chapattis* prepared from wheat flour fortified with vitamin A (retinyl palmitate, 10,000 IU/kg flour), iron (electrolytic elemental iron, 66 mg/kg flour) and few other vitamins and minerals and consumed by the apparently healthy, rural, school aged children daily for six months will demonstrate an impact in serum concentrations of retinol, ferritin and transferrin receptor (TfR) and may show a change in hemoglobin concentration. The composition of the fortified flour and contribution of the fortificant micronutrients to RDA is shown in **Table**.

The wheat flour (Atta) will be produced by a local flour mill and fortified fresh as a “batch” process at a local pharmaceutical company. The quality assurance will be maintained by the fortifying company and also samples tested by another laboratory (Institute of Nutrition and Food Science, Dhaka University). The supplied flour will be kept in a well ventilated dry room and be used within 2-3 weeks.

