#### RANDOMIZATION, WHEAT FLOUR DISTRIBUTION, CHAPATTI PREPARATION AND MONITORING:

The baris will be randomized to receive either fortified or unfortified wheat flour according to a 6 block scheme (A, B, C, D, E, F). Three of these designations will be fortified flour and three unfortified flour in a blinded manner. Containers of flour will be prepared centrally with the levels (A, B, etc.) and distributed by field assistants weekly to each of the baris according to the randomization scheme. A table of random numbers will be used to identify the required number of baris from amongst the total listed baris in the area under Mirsarai surveillance. The identified baris will then be randomized to any one of the six schemes.

The wheat flour provided will be sufficient to provide two *chapattis* to all individuals from 6 to 15 years of age. The *chapattis* will be prepared by bari mothers using the flour provided and preferably with hot water.

Twenty chapattis will be made from one kg of flour. Two chapattis (100g flour) will be given to each child in the study daily. Our pretest reveal that two chapattis made from 100g flour were consumed by all participants except one and well acceptable when provided with a condiment (halwa made from suji and sugar).

A written record of chapatti consumption will be maintained at the home by another assigned bari person, and spot checks will be made by field assistants at least twice monthly to validate that chapattis have been distributed and consumed by the participants. In addition, supervisors and one investigator will monitor the whole process of flour distribution including storage, preparation, consumption and recording at the household level at least once a month. The amount of flour distributed will also be recorded and amount remaining at the weekly visit will be recorded in order to ensure that the flour is being used. Spot check samples of flour from the bari mother will be saved for vitamin A and iron assays to verify that the flour being used is the same as that which is being distributed. When these samples are tested, care will be taken to code the samples in a way to protect the double-blinded nature of the study.

 Although the baris could be divided into two groups (A and B), this plan could more easily unblind the code, and the six codes will protect unwisely attempting to unblind the code.

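### Baris are randomised, but the Data Analysis section names only standard tests with no provision for bari; read at child level, these exceed the 5% error rate by an amount that depends on an unstated ICC

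*Protocol*

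**What the plan says.** Three sections of the protocol bear on this.

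- **Design.** Research Design and Methods states: "This is planned as a cluster-randomized, double-blind, controlled trial in a rural area in Mirsarai thana". The same section makes the bari the sampling unit, and the randomisation section allocates baris, not children, to the six flour codes. Within a bari, one woman cooks for all participating children from one coded flour supply.
- **Sample size.** The two calculations give 83 (retinol) and 87 (ferritin) subjects per group at 5% significance and 90% power. Then "the calculated sample size has been doubled to 175 in each group to account for cluster and dropout effects". At 4 eligible children per bari this becomes 44 baris per arm. No ICC, design effect or dropout rate is given.
- **Analysis.** The Data Analysis section says "Means of continuous variables, if normally distributed, will be compared by Student's t test", with Mann-Whitney for non-normal data. It adds: "Difference in categorical variables will be assessed by chi-square test". Confounding is handled by multiple regression, and final levels are compared by analysis of covariance allowing for initial or 3-month levels. It mentions no bari-level summary, random effect, GEE, cluster-robust variance or design effect.

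**The concern.** The design and the sample size recognise clustering, and the analysis drops it. Children in one bari share a cook, a flour code and a consumption recorder, and some will share a household, so their retinol and iron values are likely to be positively correlated. Applied to individual children, each named method assumes independent observations. It would understate the standard error of the arm difference, giving p-values that are too low and confidence intervals that are too narrow. This touches the primary outcome (serum retinol at 6 months) and the secondary ones (ferritin, TfR and hemoglobin). The protocol intends the results to inform fortification programmes and government policy, so a borderline result that looks firmer than it is would matter.

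**Working it through.** **Inputs from the protocol.** 44 baris per arm, 4 children per bari, 5% significance, 90% power. Retinol 29.2 (SD 10.2) and 34.2 (SD 9.5) µg/dL; ferritin 18.01 (SD 13.8) and 25.2 (SD 15.3) µg/L. **Assumed, because the protocol is silent:** two-sided testing, the ICC, the dropout rate and the spread of bari sizes.

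**1. The protocol's own sample size.** Its formula is 2 × SD² × factor / difference², with factor 10.5 for two-sided 5% and 90% power, and SD² the mean of the two variances.
- Retinol: SD² = (10.2² + 9.5²)/2 = 97.145; 2 × 97.145 × 10.5 / 5.0² = 81.6, so 82. A t-based calculation gives 82.6, so 83, as stated.
- Ferritin: SD² = (13.8² + 15.3²)/2 = 212.265; 2 × 212.265 × 10.5 / 7.19² = 86.2, so 87, as stated.
- One-sided testing gives 67 and 71, so the stated figures are two-sided.
- 2 × 87 = 174, close to 175; 175/4 = 43.75, so 44 baris.

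The figures reproduce. 83 and 87 are numbers of independent children, and clustering enters only through the doubling.

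**2. True type I error of a child-level test.** Design effect DE = 1 + (4 − 1) × ICC. True error = 2 × [1 − Φ(1.96/√DE)]. The simulation used 44 baris of 4 per arm with no effect (20,000 runs for the t tests, 4,000 for Mann-Whitney).

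| ICC (assumed) | DE | 1.96/√DE | True error | Simulated t | Simulated Mann-Whitney |
|---|---|---|---|---|---|
| 0.01 | 1.03 | 1.931 | 5.35% | – | – |
| 0.05 | 1.15 | 1.828 | 6.8% | 7.1% | 6.7% |
| 0.10 | 1.30 | 1.719 | 8.6% | 8.5% | 8.2% |
| 0.20 | 1.60 | 1.550 | 12.1% | 12.8% | 12.8% |
| 0.30 | 1.90 | 1.422 | 15.5% | – | – |
| 0.33 | 2.00 | 1.386 | 16.6% | 16.6% | 16.4% |

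The standard error is understated by 1 − 1/√DE: 1.5% at ICC 0.01, 7% at 0.05 and 27% at 0.30. A t test on bari means stayed between 4.8% and 5.4% in the same simulations.

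**3. A benchmark from the protocol's own allowance.** If a fraction d drops out, the doubling leaves DE = 175 × (1 − d)/87.
- d = 0: DE 2.01, true error 16.7%
- d = 10%: DE 1.81, true error 14.5%
- d = 20%: DE 1.61, true error 12.2%

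**4. Sensitivity.** With 20% dropout the average is 3.2 children per bari and DE = 1 + 2.2 × ICC. The error is then 6.3%, 7.6%, 10.2% and 12.8% at ICC 0.05, 0.10, 0.20 and 0.30. Unequal bari sizes push the other way: with an assumed coefficient of variation of 0.4 and a mean of 4, it is 9.3% at ICC 0.10 and 13.6% at 0.20.

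**5. Power once bari is respected.** Effective n per arm = 44m / [1 + (m − 1) × ICC], using the protocol's effect sizes and a normal approximation.

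| ICC | Children per bari (m) | Effective n | Retinol | Ferritin |
|---|---|---|---|---|
| 0.20 | 4 | 110.0 | 96.4% | 95.5% |
| 0.33 | 4 | 88.0 | 92.0% | 90.6% |
| 0.33 | 3.2 | 81.2 | 89.8% | 88.2% |

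**The case against.** **The unit of analysis is not stated.** The Data Analysis section never says that children are treated as independent, and a Student's t test on bari means would be valid. This stands as far as it goes: child level is the natural reading, not the protocol's wording. But the sample size is counted in subjects, enrolment is planned as 350 children, and bari means appear nowhere. If they were intended, the text must say so.

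**A statistical analysis plan could settle it.** The choice between a random effect and GEE can be left to such a plan, which is not at hand. But this is not silence: the protocol names its tests, and a plan that followed them would carry the error forward. The funder's review appended to the protocol asks for statistical input and control of baseline levels, but does not raise clustering.

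**The size is unknown.** A reader might infer that the error rate is certainly far above 5%. The documents do not support that, because they give no ICC and at 0.01 the excess is only about a third of a percentage point. Dropout reduces it, and the planned baseline adjustment may lower the residual ICC, though neither removes the clustering. A reader might also infer that any significant result would be spurious. That does not follow either: a small p-value can survive adjustment, and the results at risk are those near the threshold.

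**The chi-square test is peripheral.** The outcomes named in Specific Aims are all continuous, so no named endpoint depends on it. Baseline p-values likewise do not carry the trial's conclusion.

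**Conclusion.** The analysis is wrong as written for this design. Baris are randomised and the sample is enlarged partly for clustering, but the named tests make no provision for bari. On the child-level reading, the true type I error of a nominal two-sided 5% test runs from 5.35% to 15.5% for ICC 0.01 to 0.30 with four children per bari. It is about 12% to 17% if clustering is as strong as the protocol's doubling would accommodate with 0 to 20% dropout. That second range is a benchmark and not an estimate, since the protocol does not divide the doubling between clustering and dropout. For the same reason, a reader should not infer that the doubling fully covers the wider intervals of a correct analysis; the documents support only that it covers them at least in part. The result rests on a positive ICC, roughly equal bari sizes and the child-level reading.

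**What to change.** In Data Analysis, make the primary comparison of 6-month serum retinol, and likewise the comparisons of ferritin, TfR and hemoglobin, one that respects bari:

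- a linear mixed model with a random bari intercept, or GEE or regression with standard errors clustered on bari;
- arm and the baseline value of the outcome as covariates;
- a t test on the 88 bari means as a simple check;
- the estimated ICC reported for each outcome;
- the same clustering adjustment for any categorical comparison that is made.

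**Cost.** Only analysis wording changes. Bari ID is already on the appendix data forms, so no new data are needed. Confidence intervals become somewhat wider. Under the protocol's own effect sizes, power stays near 90% up to an ICC of about 0.3, so few or no extra baris would be needed within that range.
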